Although center-based rehabilitation programs have proven benefit in terms of morbidity and mortality, they are underutilized and limited by lack of participation. A promising alternative to center-based programs is home-based programs. In these programs, patients do not need to leave their homes to exercise. Center personnel can provide indirect supervision, coaching, troubleshooting, and motivational interviewing via phone. One of the most widely available, standardized home-based programs currently available in the United States is home-based CR. Recent studies have demonstrated that home-based CR can be as beneficial as center-based CR and associated with better adherence and participation rates (Thomas RJ et al. Circulation 2019). The exercise component of CR is very similar to that of PR. Both programs are accredited by the American Association of Cardiovascular and Pulmonary Rehabilitation (AACVPR) and involve aerobic conditioning, strength training, and flexibility training. Thus, home-based CR may be a safe and viable option for patients with chronic kidney disease unable to attend a center-based program. The aim of our current study is to determine whether home-based CR will improve frailty parameters and SPPB scores in patients with varying levels of kidney function. If our hypothesis is supported by the findings of this study, a home-based exercise program could be implemented prior to kidney transplantation with the ultimate goal of improving HRQOL and transplant outcomes in kidney transplant candidates.

Purpose and Objectives

The purpose of our current study is to determine whether home-based cardiac rehabilitation is an effective intervention that will improve frailty parameters and Short Physical Performance Battery scores in patients with varying levels of kidney function. We will also determine if home-based exercise improves health-related quality of life, physical activity, and adverse outcomes, including hospitalizations and death. If our hypothesis is supported by the findings of this study, a home-based exercise program could be implemented prior to kidney transplantation with the ultimate goal of improving health-related quality of life and transplant outcomes in kidney transplant candidates in the future.

Protocol Risks/Subjects

Risk Category

Category 1: Research not involving greater than minimum risk.

Subjects

Gender:

Both

Age:

Adult (18-64 yrs), Geriatric (65+ yrs)

Ethnicity:

All Ethnicities

Primary Language:

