English

Groups to be recruited will include:

Patients

Which if any of the following vulnerable populations will be recruited as subjects?

Vulnerable populations require special protections. How will you obtain informed consent, protect subject confidentiality, and prevent undue coercion?

Pregnant woman/fetus

Will pregnant women and/or fetuses (as described in 45 CFR 46 Subpart B) be enrolled in the research?

No

Neonates

Will neonates of uncertain viability or nonviable neonates (as described in 45 CFR 46 Subpart B) be enrolled in the research?

No

Children

Will children be enrolled in the research?

No

Design/Procedure**Design**

Select one category that most adequately describes your research:

c) Pilot

Discuss the research design including but not limited to such issues as: probability of group assignment, potential for subject to be randomized to placebo group, use of control subjects, etc.

This study is a prospective interventional study, which involves use of existing and prospectively collected data. This pilot study will be conducted at Baylor College of Medicine examining the feasibility, safety, acceptability, and preliminary efficacy of home-based exercise on frailty parameters and Short Physical Performance Battery score in patients with varying levels of kidney function. We plan to accrue up to 20 adult patients with chronic kidney disease. The effects of exercise on health-related quality of life, physical activity, and adverse outcomes including hospitalizations and death, will also be explored.

Inclusion Criteria:

1. Age 18 years or older
2. Ability to consent to research
3. Chronic kidney disease (stages 1-5)
4. A Short Physical Performance Battery score ≤ 10 and/or considered frail or pre-frail according to the Fried Frailty Phenotype

Exclusion Criteria:

1. Younger than 18 years
2. Patients being evaluated for combined organ transplantation
3. Significant comorbidities that limit rehabilitation potential including pulmonary disease requiring continuous oxygen supplementation, active angina, critical aortic sclerosis, decompensated heart failure, or known ventricular arrhythmia.
4. An Short Physical Performance Battery score >10 or not considered frail or pre-frail by the Fried Frailty Phenotype
5. Non-English speaker without availability of adequate interpreter services (safety concern)
6. Failure to pass submaximal exercise test in patients not approved for kidney transplantation at our center

Procedure

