down, and flexibility exercises; review the Borg Rating of Perceived Exertion (RPE); set goals with the patient; and answer any questions they might have. The exercise physiologist will then document in the electronic medical record any warning symptoms the participant experienced during physical activity or exercise; recent hospitalizations, important medical appointments, urgent care, or emergency department visits; goals set during phone call; an individualized exercise prescription. Study personnel will then send the individualized exercise prescription to the participant via mail, portal, or email. Recommended aerobic exercises will include arm and/or leg ergometry using a pedal exerciser. Recommended resistance training will include resistance bands. Patients will be encouraged to obtain at least 30 minutes of moderate-intensity physical activity at least five days per week. Gradual increases in the volume of physical activity will be recommended over time. Participants on dialysis will be advised not to exercise after in-center hemodialysis on dialysis days (if applicable). Participants will be asked to log information regarding their exercise sessions on paper, including type, duration, and Borg RPE scale.

During the subsequent weekly phone calls, the exercise physiologist will inquire about any interim symptoms or events, answer any questions regarding the exercise program, review goals set during the previous phone call and what the patient has done to work toward those goals, and set new goals if applicable. During each weekly phone call, the exercise physiologist will review and record information from the patients exercise log and enter it into the patients electronic medical record. Information entered by exercise physiologists into the electronic medical record will also be entered into REDCap by study personnel.

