Participants will be instructed to stop exercising and sit down and rest if they develop any of the following signs: chest tightness, pressure, or pain; severe shortness of breath; light-headedness or dizziness; stomach pain; upset stomach, throwing up or a headache; pulse rate that is not normal for them; extreme fatigue; profuse sweating. They will be advised to seek emergency care (call 911) immediately for chest tightness, pressure, or pain in the chest or severe shortness of breath that does not go away within 3 to 5 minutes. Home-based exercise will be stopped if the study team feels it is no longer safe for the participant to continue exercise. If a participant experiences any of the above symptoms during or after exercising, the principal investigators will be notified. If the principal investigators determine it is no longer safe for the participant to continue the exercise program following discomfort, injury, or a medical emergency during an exercise session, the participant will be withdrawn from the study. Reasons for participant withdrawal will be recorded.

Study measures:

Participants will complete the following Short Physical Performance Battery testing and other study measures at baseline and after completion of the exercise program:

1. Fried Frailty Phenotype: The Fried Frailty Phenotype consists of a gait speed test, a grip strength test, and self-reported measures of physical activity, weight loss, and exhaustion. a. Gait speed test: The time required for the participant to walk a distance of 15 feet at a self-

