3. Kidney Disease Quality of Life Short Form (KDQOL-SF), Version 1.3: Participants will complete this 37-item questionnaire, which consists of questions regarding the patients kidney disease, their quality of life, and demographic characteristics. 4. Actigraph: Participants will be asked to wear an actigraph on their upper extremity for 7 days in a row and mail the device back to us in a prepaid envelope. The actigraph monitoring will be performed both at baseline and after completion of the exercise intervention. 5. Weight: Participants' weight will be measured on a scale.

Demographic and health information: At baseline, participants will be asked to self-report their marital status, employment status, insurance, education, income, smoking history, time on dialysis, dialysis type and location, and dialysis days. If patients do not provide this information, it will be collected from the medical record when possible. Medical information, including body mass index, cause of renal disease, previous kidney transplant, and comorbidities, will be abstracted from the participants' medical record.

Participants will be offered the option of completing questionnaires via Baylor College of Medicine iPAD, on paper, or over the phone. Participants will be able to skip any question that makes them uncomfortable or that they do not want to answer.

If a participant feels unsafe or if the study team member performing the frailty/Short Physical Performance Battery tests feels the participant is unsafe at any point during the frailty/Short Physical Performance Battery tests, the participant will not be asked to complete that measure.

End of Intervention Qualitative Survey:

Following completion of the home-based exercise program, participants will be asked to complete a qualitative/satisfaction survey. Approximately one month after completion of the exercise program, participants will be asked to complete some additional questions via phone or mail to ascertain if they are still exercising.

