A Data Transfer Agreement will be obtained between Mayo Clinic and Baylor College of Medicine so that a limited data set involving subjects from Mayo Clinic can be accessed from Baylor College of Medicine. Mayo Clinic will share the data with Baylor using encrypted email and/or Microsoft Simple Share. The limited dataset that will be shared will include demographics, dates of participation in the exercise intervention, information about the exercise intervention (i.e. duration of study phone calls, participant exercise log), study outcome data (including data from frailty assessments, body composition assessments, accelerometers, and questionnaires), and medical/laboratory information abstracted from the medical record.

Sample Size/Data Analysis

Sample Size

How many subjects (or specimens, or charts) will be used in this study?

Local: 20 Worldwide: 20

Please indicate why you chose the sample size proposed:

This is a pilot study so it doesn't require sample size calculations. However, we chose our recruitment target based on a prior study examining the impact of exercise on frailty parameters which was able to show significant differences with a similar number of study participants.

Data Analysis

Provide a description of your plan for data analysis. State the types of comparisons you plan (e.g. comparison of means, comparison of proportions, regressions, analysis of variance). Which is the PRIMARY comparison/analysis? How will the analyses proposed relate to the primary purposes of your study?

Categorical variables will be summarized as counts and percentages with continuous variables summarized via medians and interquartile ranges. Pre- and post- comparisons will be made using paired, one-sample Wilcoxon signed rank tests for continuous variables and chi-square tests for categorical variables. Differences between groups will be assessed using two-sample Wilcoxon tests for continuous variables and Fisher's exact tests for categorical variables. P-values less than 0.05 will be considered statistically significant. We will make no adjustments in the p-value for multiple hypothesis testing.

Potential Risks/Discomforts

Describe and assess any potential risks/discomforts; (physical, psychological, social, legal, or other) and assess the likelihood and seriousness of such risks:

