We expect the occurrence of adverse events to be rare. All AEs will be reported immediately to the principal investigators and properly documented. Serious Adverse Events (SAEs), Unanticipated Problems Involving Risks to Subjects or Others (UPIRTSOs), and any major protocol violations will be reported to the IRB within 5 working days of the event. AEs and any minor protocol violations will be reported at the time of the continuing review. An explanation of the event and how the event was handled will be submitted with each report. The number of complaints and the number of study participants who withdrew from the study will be reported at each continuing review along with explanations for each complaint and for each withdrawal.

There is a minimal risk of injury or discomfort during the exercise sessions, and participants may be unwilling to answer certain questions within the questionnaires. The potential risks of the study are estimated to be equivalent to daily activities.

Potential Benefits

Describe potential benefit(s) to be gained by the individual subject as a result of participating in the planned work.

There are no immediate benefits to the participants from this study. The potential benefits of this study include improved physical function for the participant.

Describe potential benefit(s) to society of the planned work.

The investigators hope is to identify whether our hypothesis of a home-based exercise program will be feasible, safe, acceptable to patients, and improve frailty parameters and Short Physical Performance Battery scores in patients with varying levels of kidney functions. And if the findings of the study support hypothesis, a home-based exercise program could be

implemented prior to kidney transplantation with the ultimate goal of improving health-related quality of life and transplant outcomes in kidney transplant candidates in future.

Do anticipated benefits outweigh potential risks? Discuss the risk-to-benefit ratio.

The expected benefits of developing a feasible and effective exercise intervention in patients with decreased physical function outweigh the possible risks.

Consent Procedures

Waiver of Consent

Will any portion of this research require a waiver of consent and authorization?

NA

Waiver of requirement for written documentation of Consent

Will this research require a waiver of the requirement for written documentation of informed consent?

NA

Consent Procedures

Who will recruit subjects for this study?

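### Acceptability is a stated aim, but the satisfaction survey is planned only after completion of the programme, so those who stop early are not surveyed

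*Combined protocol and SAP*

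**What the plan says.** The Design section gives the pilot four aims: "examining the feasibility, safety, acceptability, and preliminary efficacy of home-based exercise". The hypothesis under Potential Benefits repeats them, expecting that a "home-based exercise program will be feasible, safe, acceptable to patients, and improve frailty parameters". Acceptability is therefore an aim in two places. Purpose and Objectives is narrower. It sets out to "determine whether home-based cardiac rehabilitation is an effective intervention that will improve frailty parameters", with no mention of feasibility or acceptability.

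The satisfaction data come from the section End of Intervention Qualitative Survey: "Following completion of the home-based exercise program, participants will be asked to complete a qualitative/satisfaction survey". A second contact, by phone or mail, is also tied to completion: "Approximately one month after completion of the exercise program, participants will be asked to complete some additional questions".

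For participants who leave, the Exercise Intervention section says that if the principal investigators judge continuing unsafe, "the participant will be withdrawn from the study", and that withdrawal reasons are recorded. Potential Risks/Discomforts adds that withdrawals and complaints are counted and explained at continuing review. Neither section mentions a survey for these participants.

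Exercise data are gathered week by week: "During each weekly phone call, the exercise physiologist will review and record information from the patients exercise log". Data Analysis opens with descriptive summaries and then gives pre/post tests and group tests ("Differences between groups will be assessed using two-sample Wilcoxon tests for continuous variables and Fisher's exact tests for categorical variables"). It does not say over which participants survey answers or adherence will be summarised.

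**The concern.** Acceptability asks whether patients find the programme tolerable and worth doing. Those most likely to say no are those who give it up, and the survey as scheduled does not reach them. If satisfaction differs between completers and stoppers, a percentage among completers does not describe the patients who were offered the programme.

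This bears on the rationale. The background argues for home-based exercise because centre-based programmes suffer from poor participation. A satisfaction figure that omits those who ceased to participate is weak evidence on that question. With at most 20 participants, a few early stoppers can shift the result materially.

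**Working it through.** The plan states no acceptability, retention or adherence figure, so there is nothing to reproduce. The check has two parts.

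**1. Who gets the survey?** The survey section places it after completion. One could read this as a time point, the end of week 8, and not as a condition. But no section extends it to anyone who stopped earlier, and a participant withdrawn from the study in week 3 is no longer in it at week 8. On either reading the plan makes no provision for surveying those withdrawn.

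**2. How far could the completer figure be from the figure for everyone?**

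Inputs:
- n = 20, the planned maximum (Design; Sample Size).
- k = 4 early stoppers, so 16 completers (assumed).
- 15 of 16 completers satisfied (assumed).
- s = number of the 4 stoppers who would have said they were satisfied (unknown, 0 to 4).

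Reported under the plan: 15/16 = 93.75%, or 94%.

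Over all 20: (15 + s)/20.

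| s | Over all 20 | Completer figure minus this |
|---|---|---|
| 0 | 75% | +18.75 points |
| 1 | 80% | +13.75 |
| 2 | 85% | +8.75 |
| 3 | 90% | +3.75 |
| 4 | 95% | −1.25 |

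In general the difference is (k/n) × (satisfied share of completers − satisfied share of stoppers). Here k/n = 4/20 = 0.20. The completer figure is too high whenever stoppers are less satisfied than completers, and slightly too low only if all four stoppers are satisfied.

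Varying the assumed number of stoppers, with about 90% of completers satisfied:

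| Stoppers | Reported (completers) | Range over all 20 |
|---|---|---|
| 2 | 16/18 = 89% | 80% to 90% |
| 4 | 14/16 = 88% | 70% to 90% |
| 6 | 13/14 = 93% | 65% to 95% |
| 8 | 11/12 = 92% | 55% to 95% |

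The reported figure stays near 90% throughout, while the worst case over all 20 falls to 55%.

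**Precision.** The exact (Clopper-Pearson) 95% limits for x of n are the 2.5% point of Beta(x, n−x+1) and the 97.5% point of Beta(x+1, n−x). For 15/20 they are 50.9% to 91.3%. Retention of 16/20 would have limits of 56.3% to 94.3%.

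**Adherence, to show why the denominator should be named.** Suppose the 4 stoppers leave after week 3 and every other week is logged. Logs then cover 16 × 8 + 4 × 3 = 140 of 20 × 8 = 160 scheduled person-weeks. If 75% of recorded weeks meet the target, that is 0.75 × 140 = 105 weeks, and 105/160 = 65.6% of scheduled weeks if unlogged weeks count as not met. Both are legitimate summaries of different things, and the plan does not choose between them.

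**The case against.** The strongest reply is that the plan already learns about those who leave. Reasons for withdrawal are recorded, complaints and withdrawals are counted and explained, and symptoms are asked about at each weekly call. This stands: it would be wrong to say that nothing is known about stoppers. But a reason for leaving is not a rating on the instrument given to completers, and the two cannot be combined into one acceptability figure.

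It is also fair to say that stoppers need not be dissatisfied. Someone withdrawn on medical grounds may have liked the programme. This also stands, and it is why the worst case must be shown beside the best case.

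A reader might infer more than the documents support:

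- *That the analysis plan contains nothing but hypothesis tests.* It opens with counts, percentages, medians and interquartile ranges, which could cover survey answers and retention.
- *That feasibility too is judged only on completers.* Weekly logs and withdrawal counts include non-completers, so retention can be computed for everyone.
- *That adherence will be biased upward.* The plan names no adherence estimator, so none can be called biased. Participants also keep a paper log, so a missed call need not lose that week.
- *That feasibility must be primary, or that a pass mark is required.* Purpose and Objectives names efficacy. Which aim is primary, and whether to set a progression threshold, are for the sponsor to decide.

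**Conclusion.** The point holds for acceptability. It is an aim and part of the hypothesis, its survey is scheduled only after completion, and no section offers that survey to early stoppers. Followed as written, the plan measures acceptability on a subset that is probably favourable.

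With 4 of 20 stopping and 15 of 16 completers satisfied, the reported 94% compares with 75% to 95% over all 20. The overstatement could reach about 19 points, and there could instead be an understatement of about 1 point. Upward bias is likely but not certain. The dropout and satisfaction inputs are assumptions. If nobody stops early, the problem does not arise.

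For retention and adherence the conclusion is more limited: the data reach beyond completers, and what is needed is a stated denominator.

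**What to change.** 1. Offer the same satisfaction survey when a participant stops or is withdrawn, as well as at completion. Phone or mail will do, since the plan already uses them for the one-month questions. A participant may decline, and this is then recorded as non-response.
2. Report satisfaction, retention and adherence with all eligible participants who start the programme as the denominator, and exact 95% confidence intervals for proportions. Consent comes before frailty and SPPB eligibility testing, so the wording should exclude consented participants who prove ineligible.
3. Show survey non-response separately, with best- and worst-case bounds. Do not silently count non-responders as dissatisfied.
4. For adherence, report results over the 8 scheduled weeks alongside results over recorded weeks, and identify the weeks after withdrawal so that safety withdrawals are not mistaken for poor adherence. Prescriptions are individualised and increase over time, so state what counts as a week meeting the target.

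The cost is a few sentences in Data Analysis, one short survey to the few who stop, and possibly less favourable reported figures.

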Screening and Recruitment:

Potential participants will be identified from dialysis units, nephrology clinics, primary care clinics, or kidney transplant clinics at Baylor College of Medicine clinic. If the study team is unable to reach the patient after three attempts involving phone calls and/or portal messages, an Institutional Review Board-approved contact letter may be sent up to two times. Patients who express interest in the study will go through the informed consent process with a member of the study team, and patients wishing to participate in the study will complete written consent. If patients have not had frailty and Short Physical Performance Battery testing within the two weeks prior to consent, the study team member will perform frailty and Short Physical Performance Battery testing at baseline in a supervised setting. Patients who are not frail or pre-frail and have a Short Physical Performance Battery score > 10 will be ineligible for study participation. Patients with stage 1-5 chronic kidney disease who are not currently approved for kidney transplant at our center will undergo a submaximal exercise test to rule out any significant, undiagnosed cardiopulmonary disease if they meet one or more of the following criteria: 1) diabetes, 2) age > 59, 3) prior coronary artery disease defined as history of myocardial infarction, coronary artery stenting, or coronary artery bypass grafting, or 4) current smoking. During the initial study visit, consenting patients will be provided with a pedal exerciser, resistance bands, and exercise pamphlets (Mayo Clinic Patient Education Pulmonary Rehabilitation: Exercise Program, Exercise Program Guidelines, Exercises for the Legs). Participants will be given the option of having the pedal exerciser mailed to their home.

Exercise Intervention:

Participants will be asked to complete an 8-week home-based exercise program with a focus on the core components of physical activity counseling and exercise training according to guidelines from the American Heart Association and the American Association of Cardiovascular and Pulmonary Rehabilitation (Balady GJ Circulation 2007). During the program, participants will receive weekly semi-scripted phone calls from an exercise physiologist from the Mayo Clinic Cardiac Rehabilitation program. During the baseline phone call, the exercise physiologist will assess the patients current level of physical activity; discuss warm-up, cool-

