selected walking speed will be measured using a stopwatch. To determine whether the participant is frail by the Fried Frailty Phenotype, the average of 2 trials will be calculated and adjusted for sex and height. b. Hand grip strength test: Hand grip strength will be measured using a Jamar Digital Hand Held Dynamometer. Participants will complete the grip strength test 3 times with their dominant hand (or the arm without their dialysis fistula or graft). The 3 trials will be averaged and adjusted by sex and body mass index using a normative table. c. Minnesota Leisure-time Physical Activity Questionnaire: Participants will answer questions from this questionnaire regarding how often they engage in different activities. d. Self-reported weight loss: Patients will be asked whether they unintentionally lost 10 or more pounds within the last year. e. Center for Epidemiologic Studies Depression Scale (CES-D): Participants will answer 2 questions from the CES-D about their level of exhaustion. 2. Short physical performance battery (SPPB): The Short Physical Performance Battery consists of a gait speed test over 4 meters (13.1 feet), timed repeated chair stands, and three balance tests. a. Gait speed test: The participants gait speed velocity over 4 meters will be calculated by converting the results of the participants gait speed test (please see Fried Frailty phenotype above) to meters per second. b. Timed repeated chair stands: Participants will be asked if they feel safe to stand from a chair without the use of their arms and without assistance. If the participant feels safe to stand from a chair without the use of their arms and without assistance, they will be asked to complete 5 repeated chair stands. The participants SPPB score will be determined by the time required to complete 5 repeated chair stands. c. Balance testing: The participants balance will be tested in side-by-side, semi-tandem, and tandem stands. In the side-by-side stand, participants will stand with their feet as close together as possible. In the semi-tandem stands, participants will stand with one heel touching the big toe of the opposite foot. In the tandem stands, participants will stand with the heel of one foot in front of the toes of the other foot (as if on a balance beam). Participants will be asked to hold each position for up to 10 seconds.

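### The eligibility criteria conflict on whether one abnormal scale is enough for entry; if it is, some participants start with little room to improve, which can dilute the SPPB change and makes a Fried category comparison insensitive

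*Combined protocol and SAP*

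**What the plan says.** Under Design/Procedure, inclusion item 4 reads: "A Short Physical Performance Battery score ≤ 10 and/or considered frail or pre-frail according to the Fried Frailty Phenotype". Exclusion item 4 in the same section reads: "An Short Physical Performance Battery score >10 or not considered frail or pre-frail by the Fried Frailty Phenotype". Screening and Recruitment, repeated under Consent Procedures, says: "Patients who are not frail or pre-frail and have a Short Physical Performance Battery score > 10 will be ineligible for study participation".

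SPPB and frailty parameters are also the efficacy outcomes. A qualifying test done in the two weeks before consent need not be repeated, so the score that qualifies a patient can also be the baseline score.

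Study measures describes five Fried components, including a measured gait speed and a measured grip strength. Of chair-stand time it says: "The participants SPPB score will be determined by the time required to complete 5 repeated chair stands". Participants who do not feel safe do not attempt the chair stands.

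Data Analysis compares pre and post values by "paired, one-sample Wilcoxon signed rank tests for continuous variables and chi-square tests for categorical variables". It does not say whether frailty is analysed as a category, a count or measured components. It names no primary comparison and says nothing about participants who begin at the best score. No control group is described. On size: "We plan to accrue up to 20 adult patients with chronic kidney disease", and "This is a pilot study so it doesn't require sample size calculations".

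**The concern.** The scales that decide entry are also the scales on which benefit is judged. If one abnormal scale is enough, two kinds of participant have limited room on the other. A frail or pre-frail patient with SPPB above 10 is near the top of the SPPB. A patient with SPPB of 10 or less who is neither frail nor pre-frail is already in the best Fried category and can only stay there or worsen. Both would enter every pre/post comparison.

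With at most 20 participants and a 0.05 criterion, participants who cannot move on a scale reduce its average change and the power to detect one. For frailty there is a second loss if status is analysed as a category. A change of one item often leaves the category unchanged, and an ordinary chi-square test treats the pre and post values as independent samples.

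**Working it through.** **1. Who can enter.** Setting the three statements side by side:

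| SPPB | Fried | Inclusion item 4 | Screening text | Exclusion item 4 |
|---|---|---|---|---|
| ≤ 10 | frail or pre-frail | in | in | in |
| > 10 | frail or pre-frail | in | in | out |
| ≤ 10 | neither | in | in | out |
| > 10 | neither | out | out | out |

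The two middle rows are the patients at issue. Whether they enrol depends on how the conflict is resolved.

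**2. The plan's own figure.** The target of 20 cannot be reproduced, because no effect size, SD, power or dropout rate is given. For scale only, the paired effect detectable with 80% power at two-sided 0.05 is (1.960 + 0.842)/√20 = 0.63 SD. With a signed-rank efficiency of 0.955 it is 2.802/√(20 × 0.955) = 0.64 SD.

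**3. Ceiling alone.** Assume a fraction f of participants sits at the best score and does not change, while the rest change by a mean of 1 point (SD 1.5, rounded). The expected mean change is (1 − f) × 1. Simulated signed-rank power at n = 20:

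| f | 0% | 10% | 20% | 30% | 40% | 50% |
|---|---|---|---|---|---|---|
| Mean change | 1.0 | 0.9 | 0.8 | 0.7 | 0.6 | 0.5 |
| Power | 80% | 71% | 68% | 62% | 52% | 44% |

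This isolates the mechanism. It leaves out measurement error at entry.

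**4. Ceiling with selection on a noisy score.** All of these inputs are assumptions:
- SPPB maximum 12, population mean 9, 10 or 11, SD 2.
- Fried count 0-5 with 0 meaning not frail, mean 1.3, SD 1.2.
- Correlation between the scales 0.5.
- Retest reliability 0.70, 0.85 or 0.95.
- The entry score is the baseline score.

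Results under the either-scale rule, as ranges over the three reliabilities (a positive Fried change is improvement):

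| Population SPPB mean | 9 | 10 | 11 |
|---|---|---|---|
| Entering with SPPB > 10 | 13-15% | 28-30% | 49-50% |
| Entering at SPPB 12 | 5-6% | 14-16% | 30-32% |
| SPPB change, true gain 1.0 | 0.97-1.00 | 0.88-0.90 | 0.71-0.72 |
| SPPB change, no true gain | 0.02-0.07 | 0.02-0.07 | 0.02-0.06 |
| Entering at Fried 0 | 16-17% | 11-12% | 6-7% |
| Fried change, true gain 0.5 | 0.46-0.47 | 0.49-0.51 | 0.52-0.55 |
| Fried change, no true gain | 0.01-0.04 | 0.03-0.07 | 0.04-0.11 |

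SPPB dilution is (1.00 − observed)/1.00, which runs from 0% to (1.00 − 0.71)/1.00 = 29%. For the Fried count the deviation from truth runs from (0.46 − 0.50)/0.50 = −8% to (0.55 − 0.50)/0.50 = +10%.

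**5. If both deficits are required.** The same model gives SPPB changes of 1.04 to 1.41 for a true gain of 1.0, and 0.04 to 0.54 for no true gain. Fried changes are 0.53 to 0.61 for a true gain of 0.5. The ceiling has gone, but regression to the mean now overstates the gain.

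**6. How frailty is tested.** In step 4, with a true gain of 0.5 item, the signed-rank test on the count has 54% to 97% power. A separate run of both tests under assumed inputs gave about 58-93% for the signed-rank test on the count and 7-34% for the chi-square on category. The category cut-offs used there are also assumed.

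**The case against.** The strongest reply is that exclusion item 4, taken literally, leaves nobody with a normal score on either scale, so the problem disappears. That stands as a reason to reconcile the criteria first. It does not dispose of the point, because the inclusion criterion and the screening text, which appears twice, say otherwise.

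A reader might infer that both headline outcomes are understated and pulled toward no benefit. A simulation that treats the baseline as error-free supports that impression: with 30% of participants at 11-12 and a true gain of 1, it gives a mean change of +0.68, about 58% power, and a drift of −0.13 when nothing has changed. The documents do not support it as a conclusion. Patients are chosen for a poor score, that score can be the baseline, and there is no control group, so regression to the mean works in the opposite direction. Once it is allowed for, about 30% entering above 10 gives +0.88 to +0.90, and the no-effect drift is slightly positive. Nor is it right that everyone above 10 cannot improve: on the assumed 12-point scale, a score of 11 can still gain a point.

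It is also fair that frailty parameters may already cover gait speed and grip as measured values, which the signed-rank test would handle. Data Analysis does not say so, and chair-stand time is described only as an input to the SPPB score.

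Making the raw measures the lead outcomes instead of SPPB would be a debatable trade. It would displace a named efficacy outcome, and participants who cannot safely do the chair stands have no time to analyse.

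Finally, this is a pilot of feasibility, safety and acceptability with preliminary efficacy, and broad entry is a legitimate choice. That limits the weight of the point, but the plan still tests efficacy at 0.05.

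**Conclusion.** The point holds in a limited form. The eligibility statements contradict each other and must be reconciled; the documents do not settle which is intended. Under the either-scale reading, the SPPB change can be diluted by about 0 to 29% of an assumed 1-point gain. The size depends on how many participants start near the top, which the plan does not give.

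For the Fried count the net effect is small and of uncertain sign (−8% to +10% of an assumed 0.5-item gain), so a claim that frailty results are understated is not supported. The firmer frailty problem is the choice of test. If status is compared as a category by chi-square, the pairing and the within-category change are lost, and under the assumed inputs most of the power goes with them.

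The percentages rest on assumed scale limits, population means, reliabilities and gains. They show plausible size and are not estimates for this trial.

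**What to change.** First, reconcile inclusion item 4, exclusion item 4 and the screening text so that they state one rule.

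Then, in Data Analysis:
- Keep SPPB total as a named efficacy outcome.
- Analyse Fried as the 0-5 item count with the paired signed-rank test, in place of a chi-square on category. Still report the category descriptively.
- Report gait speed (m/s), grip strength (kg) and chair-stand time (s) pre and post alongside SPPB. Rank participants unable to do the chair stands as worst; do not drop them.
- Report how many participants were at the best possible score on each scale at baseline.
- For each scale, add a supporting analysis in participants with a deficit on that scale. State that this subset is more exposed to regression to the mean, so it does not replace the analysis of all participants.

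No extra visits, patients or procedures are needed, because the measurements are already taken. The cost is a few more analyses without multiplicity adjustment, and a frailty measure less familiar to readers than the category.
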